ULN	upper limit of normal
WHO	World Health Organization
SD	standard deviation
SOC	system organ class
TEAE	treatment-emergent adverse event
TFLs	tables, figures, and listings
ULN	upper limit of normal
WHO	World Health Organization

PHARMACOKINETIC ABBREVIATIONS

AUC	area under the concentration versus time curve
AUC ₀₋₁₂	partial area under the concentration versus time curve from time "x" to time "xx"
C _{max}	maximum observed concentration of drug
C _{trough}	concentration at the end of the dosing interval

1. INTRODUCTION

This statistical analysis plan (SAP) describes the statistical analysis methods and data presentations to be used in tables, figures, and listings (TFLs) in the clinical study report (CSR) for Study GS-US-611-6464. This SAP is based on the study protocol original dated 09 May 2023, study protocol administrative amendment 1 dated 22 June 2023, study protocol amendment 0.1 EU dated 15 November 2023 and the electronic case report form (eCRF). The SAP will be finalized before database finalization. Any changes made after the finalization of the SAP will be documented in the CSR.

This study was terminated early; hence only the analyses outlined in this SAP will be performed.

1.1. Study Objectives and Endpoints

Primary Objective(s)	Primary Endpoint(s)

To evaluate the plasma pharmacokinetics (PK) of ODV in pediatric participants with COVID-19To evaluate the safety and tolerability of ODV in pediatric participants with COVID-19	
PK parameters (AUC_{0-12}, C_{max}, and C_{trough}) for ODV metabolite, GS-441524Incidence of treatment-emergent adverse events (AEs) by Day 35Incidence of treatment-emergent laboratory abnormalities by Day 35
Secondary Objective(s)	Secondary Endpoint(s)

To assess the impact of ODV on time to sustained alleviation of targeted COVID-19 symptoms in pediatric participants with COVID-19To evaluate the antiviral activity of ODV on SARS-CoV-2 nasal swab viral load in pediatric participants with COVID-19To assess the impact of ODV on the requirement for supplemental oxygen in pediatric participants with COVID 19To evaluate palatability and acceptability of ODV in pediatric participants with COVID-19	
Time to sustained alleviation of targeted COVID-19 symptoms by Day 35Change from baseline in SARS-CoV-2 nasal swab viral load at Day 5Proportion of participants who require supplemental oxygen support (low flow oxygen, high flow oxygen, noninvasive ventilation, mechanical ventilation, or extracorporeal membrane oxygenation) by Day 35Assessment of palatability and acceptability scores of each formulation at Day 5

• To provide data on the use of medications other than remdesivir (RDV) and ODV for treatment of COVID-19 in pediatric participants with COVID-19• To assess the impact of ODV on COVID-19-related hospitalizations or all-cause death in pediatric participants with COVID-19	
• Proportion of participants with concomitant use of medications other than RDV and ODV for treatment of COVID-19 by Day 35• Proportion of participants with COVID-19-related hospitalization or all-cause death by Day 35
---	---

CCI

1.2. Study Design

This is a Phase 2/3, single-arm, multi-cohort, open-label study to evaluate the safety, PK, and efficacy of ODV in pediatric participants with COVID-19 who are at risk of progression to severe disease.

At least 52 participants aged 0 days to < 18 years were planned to be enrolled as described in [Table 1-1](#). Participants were enrolled in a staggered manner and received treatment with ODV. Cohorts were opened for enrollment based upon availability of a suitable pediatric formulation and availability of preliminary safety and PK data.

Table 1-1. Study Design

Cohort	Description	Dose	Number of participants
Pediatric participants ≥ 28 days to < 18 years old			
1	≥ 6 years to < 18 years and weight ≥ 40 kg	ODV CCI administered orally BID for 5 days	12
2	≥ 6 years to < 18 years and weight ≥ 20 kg to < 40 kg	ODV CCI administered orally BID for 5 days	12
3	≥ 2 years to < 18 years and weight ≥ 12 kg to < 20 kg	TBC	12
4	≥ 28 days to < 18 years and weight ≥ 3 kg to < 12 kg	TBC	12
Term neonatal participants 0 days to < 28 days old			
5	≥ 14 days to < 28 days of age, GA ≥ 37 weeks and weight ≥ 2.5 kg	TBC	≥ 4
6	0 days to < 14 days of age, GA ≥ 37 weeks and birth weight ≥ 2.5 kg	TBC	All available
Preterm neonates and infants 0 days to < 56 days old			
7	0 days to < 56 days of age, GA < 37 weeks and birth weight ≥ 1.5 kg	TBC	All available

GA = gestational age; TBC = To be confirmed.

Participants had to have:

- SARS-CoV-2 infection confirmed by polymerase chain reaction or an alternative molecular diagnostic assay
- Initial onset of COVID-19 signs/symptoms ≤ 5 days before screening with ≥ 1 sign/symptom
- Presence of ≥ 1 characteristic or underlying medical condition associated with an increased risk of developing severe illness due to COVID-19

Randomization and treatment codes were not applicable in this study. Blinding of treatment assignments or data was not applicable in this study.

The study treatment period was 5 days with a posttreatment follow-up period of 30 days after the last dose of study drug.

The schedule of study procedures is presented in [Appendix 1](#).

1.3. Sample Size and Power

The total sample size was planned to be at least 52 participants.

A minimum of 12 evaluable participants from each cohort (Cohorts 1–4) provides > 90% power to reject the null hypothesis that there is at least a 30% difference in GS-441524 AUC₀₋₁₂ and C_{max}, respectively, between pediatric and adult participants, using 2 one-sided tests with each performed at an alpha level of 0.05. This power analysis assumes that the expected geometric mean ratio between the pediatric participants versus the adult group is 1, the equivalency boundary is 70% to 143%, and the interparticipant standard deviation (SD) of AUC₀₋₁₂ and C_{max} are 0.19 h·ng/mL and 0.18 ng/mL respectively (natural log scale, preliminary results from Study GS-US-611-6248).

The sample size calculation was performed using SAS® Software Version 9.4.

This study was terminated early; hence the number of participants originally planned to be enrolled as outlined above was not achieved.

2. TYPE OF PLANNED ANALYSIS

2.1. Interim Analyses

As the study has been terminated early, interim analyses are no longer required.

2.1.1. Dose Selection Analysis

As the study has been terminated early, dose selection analyses for additional cohorts are no longer required.

2.1.2. Data Monitoring Committee Analyses

As the study has been terminated early, data monitoring committee (DMC) analyses are no longer required.

2.2. Final Analysis

The final analysis will be performed after all participants enrolled at the time of study termination have completed the study, outstanding data queries have been resolved or adjudicated as unresolvable, and the data have been cleaned and finalized.

2.3. Changes from Protocol-Specified Analyses

This study was terminated early; hence only the analyses outlined in the subsequent sections will be performed.

3. GENERAL CONSIDERATIONS FOR DATA ANALYSES

Due to the low number of participant in the study at the time of early termination, no tables or figures will be provided for this study.

By-participant listings will be presented for all participants in the All Enrolled Analysis Set and sorted by cohort, participant identifier (ID) number in ascending order, visit date, and time (if applicable), unless otherwise specified. Data collected on log forms, such as AEs, will be presented in chronological order within the participant. The cohort to which participants were enrolled will be used in the listings. Age, sex at birth, race, and ethnicity will be included in the listings, as space permits.

3.1. Analysis Sets

Analysis sets define the participants to be included in an analysis. Analysis sets and their definitions are provided in this section. The analysis set will be identified and included as a subtitle of each TFL.

3.1.1. All Enrolled Analysis Set

All Enrolled Analysis Set includes all participants who received a study participant ID number in the study after screening.

3.1.2. Full Analysis Set

The Full Analysis Set (FAS) includes all enrolled participants who took at least 1 dose of study drug. This is the primary analysis set for efficacy analyses.

3.1.3. Safety Analysis Set

The Safety Analysis Set includes all participants who took at least 1 dose of study drug. This is the primary analysis set for safety analyses.

3.1.4. Pharmacokinetic Analysis Set

The PK Analysis Set will include all enrolled participants who took at least 1 dose of study drug and have at least 1 nonmissing concentration value reported by the PK laboratory for GS-441524. This is the primary analysis set for all PK analyses. Within the PK Analysis Set, those participants with PK exposure data successfully derived from the population PK (PopPK) modeling will be included in the analyses related to PK exposure.

3.1.5. Virology Analysis Set

The Virology Analysis Set will include all enrolled participants who took at least 1 dose of study drug and have a baseline SARS-CoV-2 viral load \geq lower limit of quantification (LLOQ). Refer to Section 3.7 for the definition of LLOQ.

3.2. Participant Grouping

For analyses, participants will be grouped according to the cohort to which participants were enrolled.

3.3. Strata and Covariates

This study is not randomized. It therefore did not use a stratified randomization schedule when enrolling participants. No covariates will be included in efficacy and safety analyses.

3.4. Examination of Participant Subgroups

There are no prespecified participant subgroupings for efficacy and safety analyses.

3.5. Multiple Comparisons

Adjustments for multiplicity will not be made, because no formal statistical testing will be performed in this study.

3.6. Missing Data and Outliers

3.6.1. Missing Data

In general, missing data will not be imputed unless methods for handling missing data are specified. Exceptions are presented in this document.

For missing last dosing date of study drug, imputation rules are described in Section 4.2. The handling of missing or incomplete dates for AE onset is described in Section 7.1.5.2, and for prior and concomitant medications in Section 7.3.

3.6.2. Outliers

Outliers of non-PK data will be identified during the data management and data analysis process, but no sensitivity analyses will be conducted. All data will be included in the data analysis.

3.7. Data Handling Conventions and Transformations

The following conventions will be used for the imputation of date of birth when it is partially missing or not collected:

- If only month and year of birth is collected, then “15” will be imputed as the day of birth
- If only year of birth is collected, then “01 July” will be imputed as the day and month of birth
- If year of birth is missing, then date of birth will not be imputed.

In general, age collected at Day 1 will be used for analyses and presented in listings. If age at Day 1 is not available for a participant, then age derived based on date of birth and the Day 1 visit date will be used instead. If an enrolled participant was not dosed with any study drug, the enrollment date will be used instead of the Day 1 visit date. For screen failures, the date the first informed consent was signed will be used for the age derivation. Age required for longitudinal and temporal calculations and analyses (for eg, estimates of creatinine clearance, age at date of AE) will be based on age derived from date of birth and the date of the measurement or event, unless otherwise specified.

Non-PK data that are continuous in nature but are less than the LLOQ or above the upper limit of quantitation (LOQ) will be imputed as follows:

- A value that is 1 unit less than the LLOQ at the same precision level of the originally reported value will be used to calculate descriptive statistics if the datum is reported in the form of “ $< x$ ” (where x is considered the LLOQ). For eg, if the values are reported as < 50 and < 5.0 , values of 49 and 4.9, respectively, will be used to calculate summary statistics. An exception to this rule is any value reported as < 1 or < 0.1 , etc. For values reported as < 1 or < 0.1 , a value of 0.9 or 0.09, respectively, will be used to calculate summary statistics.
- A value that is 1 unit above the upper LOQ will be used to calculate descriptive statistics if the datum is reported in the form of “ $> x$ ” (where x is considered the upper LOQ). Values with decimal points will follow the same logic as above.
- The lower or upper LOQ will be used to calculate descriptive statistics if the datum is reported in the form of “ $\leq x$ ” or “ $\geq x$ ” (where x is considered the lower or upper LOQ, respectively).

SARS-CoV-2 viral load results that are below LLOQ but have a positive signal will be reported as “ < 2228 cp/mL SARS-CoV-2 detected” and those that are below the lower limit of detection (LOD) and negative will be reported as “No SARS-CoV-2 detected”. The data will be imputed as follows:

- A value of 1114 copies/mL (half of the LOQ 2228 copies/mL) will be used to calculate descriptive statistics if the datum is reported as “ < 2228 cp/mL SARS-CoV-2 detected”.
- A value of 746.5 copies/mL (half of the LOD 1493 copies/mL) will be used to calculate descriptive statistics if the datum is reported as “No SARS-CoV-2 detected”.

Base 10 logarithm transformation will be used for analyzing SARS-CoV-2 viral load.

Sparse PK concentration values that are below the limit of quantitation (BLQ) will be presented as “BLQ” in the data listing.

3.8. Analysis Visit Windows

3.8.1. Definition of Study Day

Study day will be calculated from the first dosing date of study drug and derived as follows:

- For postdose study days: Assessment Date – First Dosing Date + 1
- For days prior to the first dose: Assessment Date – First Dosing Date

Therefore, Study Day 1 is the day of first dose of study drug administration.

Last Dose Date is defined as the maximum, nonmissing, nonzero dose end date of treatment recorded on the Study Drug Administration eCRF with “Check box if study drug was permanently withdrawn” checked for participants who prematurely discontinued or completed study drug according to the Study Drug Completion eCRF. Refer to Section 4.2 for missing date imputation, if necessary.

Last Study Date is the latest of the study drug start dates and end dates, the in-person or virtual visit dates, the vital sign collection dates, the participant and/or caregiver COVID-19 symptom assessment questionnaire dates, the laboratory collection dates, and the death date (if applicable, for participants who died during the study, the death date will be the Last Study Date. For participants who died after completing the study or after prematurely discontinuing the study, the death date will not be considered for the Last Study Date).

Baseline value is defined as the last value obtained on or prior to the first dose of study drug administration date unless otherwise specified (see Section 3.8.3).

3.8.2. Analysis Visit Windows

Participant visits might not occur on protocol-specified days. Therefore, for the purpose of analysis, observations will be assigned to analysis windows.

The analysis windows for chemistry laboratory tests, hematology laboratory tests, and vital signs are provided in [Table 3-1](#).

Table 3-1. Analysis Visit Windows for Chemistry Laboratory Tests, Hematology Laboratory Tests, and Vital Signs

Visit	Study Day	Visit Window Study Day	
		Lower Limit	Upper Limit
Baseline	1	(none)	1
Day 3	3	2	4
Day 5	5	5	20
Day 35	35	21	≥ 35

Hematology laboratory tests include complete blood count (CBC) with differential. Chemistry laboratory tests include albumin, alanine aminotransferase (ALT), alkaline phosphatase (ALP), aspartate aminotransferase (AST), total bilirubin, blood urea nitrogen, creatinine, estimated glomerular filtration rate (eGFR) using bedside Schwartz formula, ionized calcium, carbon dioxide, chloride, total serum protein, potassium, and sodium. Vitals signs include heart rate, temperature, blood pressure (mean arterial pressure [MAP] if available, systolic and diastolic), respiratory rate, and oxygen saturation.

The analysis windows for coagulation laboratory tests are provided in [Table 3-2](#).

Table 3-2. Analysis Visit Windows for Coagulation Laboratory Tests

Visit	Study Day	Visit Window Study Day	
		Lower Limit	Upper Limit
Baseline	1	(none)	1
Day 5	5	2	≥ 5

Coagulation laboratory tests include prothrombin time (PT), activated partial thromboplastin time (aPTT) with calculated international normalised ratio (INR).

The analysis windows for urinalysis laboratory tests are provided in [Table 3-3](#).

Table 3-3. Analysis Visit Windows for Urinalysis Laboratory Tests

Visit	Study Day	Visit Window Study Day	
		Lower Limit	Upper Limit
Baseline	1	(none)	1

Urinalysis laboratory tests include bilirubin, glucose, erythrocytes, and leukocytes.

The analysis windows for SARS-CoV-2 midturbinate nasal swab and microbiology laboratory tests are provided in [Table 3-4](#).

Table 3-4. Analysis Visit Windows for SARS-CoV-2 Midturbinate Nasal Swab and Microbiology Laboratory Tests

Visit	Study Day	Visit Window Study Day	
		Lower Limit	Upper Limit
Baseline	1	(none)	1
Day 3	3	2	4
Day 5	5	5	6
Day 8	8	7	11
Day 14	14	12	25
Day 35	35	26	≥ 35

Microbiology laboratory tests include Influenza A Virus, Influenza B Virus, Respiratory Syncytial Virus (RSV), and SARS-CoV-2.

3.8.3. Selection of Data in the Event of Multiple Records in an Analysis Visit Window

Depending on the statistical analysis method, single values may be required for each analysis window. For example, change from baseline by visit usually requires a single value, whereas a time-to-event analysis would not require 1 value per analysis window.

If multiple valid, nonmissing measurements exist in an analysis window, records will be chosen based on the following rules if a single value is needed:

- For baseline data, the last nonmissing value on or prior to the first dose of study drug administration date will be selected, unless specified differently. If there are multiple records on the same day, the baseline value will be selected as follows:
 - For continuous data:
 - For SARS-CoV-2 viral load data, the geometric mean (copies/mL) will be taken.
 - For other continuous data, the average of the measurements will be taken.
 - For categorical data:
 - For SARS-CoV-2 infection status, the highest severity (ie, a positive PCR result) will be selected.
 - For other categorical data, the lowest severity will be selected.

- For postbaseline values:
 - The record closest to the nominal day for that visit will be selected with the exception of SARS-CoV-2 viral load data in which the latest record will be selected.
 - If there are 2 records that are equidistant from the nominal day, the later record will be selected.
 - If there is more than 1 record on the selected day, values will be selected as follows:
 - For SARS-CoV-2 viral load, if there are multiple records with the same time or no time recorded on the same day, the geometric mean value (copies/mL) will be taken.
 - For red blood cell (RBC) Morphology result, if there is more than 1 record on the selected day, all results will be selected.
 - For other parameters, if there is more than 1 record on the selected day, the average will be taken for continuous data and the worst severity will be taken for categorical data, unless otherwise specified.

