5.2. Other Baseline Characteristics

Other baseline characteristics include:

- Duration of COVID-19 symptoms prior to first dosing date (days)
 - Defined as: First Dosing Date – Onset Date of First/Earliest COVID-19 Symptom
- Duration from first positive SARS-CoV-2 diagnostic test to first dosing date (days)
 - Defined as: First Dosing Date – Date of COVID-19 Diagnosis
- Risk factors linked to medical history:
 - **CCI**

- Total number of risk factors
- Baseline COVID-19 vaccination status: (a) Yes; (b) No
- Baseline respiratory viral coinfections: (a) None; (b) Yes subdivided into: (i) Influenza A; (ii) Influenza B; (iii) RSV
- Baseline SARS-CoV-2 viral load (as a continuous variable, and a categorical variable: (a) $< 6 \log_{10}$ copies/mL; (b) $\geq 6 \log_{10}$ copies/mL)
- Baseline eGFR using the bedside Schwartz formula (mL/min/1.73 m²)
- Baseline ALT (U/L)

A by-participant listing of other baseline characteristics will be provided by participant ID number (in ascending order).

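### Conflicting same-day baseline influenza or RSV results are resolved to negative, so a coinfection detected on the baseline day can be listed as 'None'

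*SAP*

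**What the plan says.** SAP Section 3.8.3 covers several valid records falling in one analysis window. Its rules apply only when one value has to be chosen: "records will be chosen based on the following rules if a single value is needed".

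- **Baseline, same day, SARS-CoV-2 status:** "For SARS-CoV-2 infection status, the highest severity (ie, a positive PCR result) will be selected".
- **Baseline, same day, every other categorical result:** "For other categorical data, the lowest severity will be selected".
- **Postbaseline, more than one record on the selected day:** "the worst severity will be taken for categorical data, unless otherwise specified".

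Section 3.8.2 (text below Table 3-4) places the respiratory viruses in one group with one set of windows: "Microbiology laboratory tests include Influenza A Virus, Influenza B Virus, Respiratory Syncytial Virus (RSV), and SARS-CoV-2".

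Section 5.2 defines the affected variable: "Baseline respiratory viral coinfections: (a) None; (b) Yes subdivided into: (i) Influenza A; (ii) Influenza B; (iii) RSV". It also states how the variable is shown: "A by-participant listing of other baseline characteristics will be provided by participant ID number (in ascending order".

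**The concern.** The SARS-CoV-2 bullet treats a positive result as the higher severity. On that scale, lowest severity for a positive/negative test means negative. Four viruses handled as one group of tests thus get opposite tie rules: a positive wins for SARS-CoV-2, and a negative wins for the other three.

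Taking the lowest severity at baseline is a reasonable convention for graded safety data, because it keeps a later worsening visible. A coinfection test is a diagnosis, not a grade from which worsening is measured, so that reason does not carry over. Here the rule discards a detection.

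At stake is the accuracy of one column in a by-participant listing. Section 3 plans no tables or figures because few children were enrolled, so each child's row is what a reader has when interpreting symptoms, adverse events and viral load. The visible text offers no other listing from which the discarded positive could be recovered. Section 7.2 lists hematology, serum chemistry and coagulation, and the visible part of Section 6.2 lists SARS-CoV-2 viral load but no influenza or RSV results. Part of the efficacy section is redacted, so this last point covers visible text only.

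**Working it through.** The plan gives no figure on this point, so there is none to reproduce. The check applies the rules to a case and then illustrates the size under stated assumptions.

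**Step 1. Is a single value needed?** Yes. The Section 5.2 variable is None/Yes by virus, so each virus needs one baseline status.

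**Step 2. Apply Section 3.8.3 to one negative and one positive result on the same baseline day, with the other coinfection viruses negative.**

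| Test | Rule | Selected | Section 5.2 entry |
|---|---|---|---|
| SARS-CoV-2 | highest severity | positive | not applicable |
| Influenza A, influenza B or RSV | lowest severity | negative | 'None' |
| Influenza A, influenza B or RSV, if changed to highest severity | highest severity | positive | 'Yes' |

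No exception for the coinfection viruses appears in the visible text.

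**Step 3. How often can it arise?** All of the following must hold: two valid results for the same virus, on the same day, that disagree. Appendix 1, footnote a, says that shared assessments are not repeated when Screening and Day 1 fall on one calendar day. If the swabs fall on different days, the tie rule does not apply and the last value on or before the first dosing date is used.

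**Step 4. Size in a truly coinfected child with two same-day results.** Assumptions, not in the documents: independent results, each with sensitivity s.

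- Discordant: 2s(1 − s)
- Listed positive under lowest severity: s²
- Listed positive if any positive counts: 1 − (1 − s)²

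| s | Discordant | Lowest severity | Any positive |
|---|---|---|---|
| 0.70 | 0.42 | 0.49 | 0.91 |
| 0.80 | 0.32 | 0.64 | 0.96 |
| 0.90 | 0.18 | 0.81 | 0.99 |
| 0.95 | 0.095 | 0.90 | 0.998 |

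Under the SAP rule a second test lowers detection below that of one test (for example 0.64 against 0.80). Positively correlated same-day results would narrow the gap.

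**Step 5. The opposite error.** Step 4 concerns coinfected children only, so false positives play no part in it. Now assume prevalence 2%, s = 0.90 and specificity c, with two independent tests. The probability that a listed positive is true is:

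- Any positive, c = 0.98: 0.02 × 0.99 / (0.02 × 0.99 + 0.98 × (1 − 0.98²)) = 0.0198 / 0.0586 ≈ 34%
- Lowest severity, c = 0.98: 0.02 × 0.81 / (0.02 × 0.81 + 0.98 × 0.02²) = 0.0162 / 0.0166 ≈ 98%
- Any positive, c = 0.995: 0.0198 / (0.0198 + 0.98 × (1 − 0.995²)) = 0.0198 / 0.0296 ≈ 67%
- Lowest severity, c = 0.995: 0.0162 / (0.0162 + 0.98 × 0.005²) = 0.0162 / 0.01622, above 99%

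So the any-positive rule misses fewer true coinfections and lists more false ones. How many more depends on prevalence and specificity, which the documents do not give.

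**The case against.** **SARS-CoV-2 can properly be treated differently.** Confirmed SARS-CoV-2 infection is an entry requirement (Section 1.2), so letting any positive count fits that variable. Coinfection is only descriptive: Section 3.3 uses no covariates and Section 3.4 no subgroups. This stands as a reason why the two rules may differ. It does not supply a reason for discarding a positive coinfection result.

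**Some discordant pairs are false positives.** For those, the SAP rule gives the right answer. This stands. A reader might infer that every discordant pair is misclassified, but that holds only if false positives are assumed away. Which error to prefer is a judgement.

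**The case is rare.** This also stands. Nothing in the SAP shows that even one such pair is expected among the few children enrolled.

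**The direction reverses after baseline.** Because postbaseline ties take the worst severity, a reader might infer that a virus present at baseline would be reported as newly acquired on treatment. The visible plan does not support this:

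- Treatment-emergent adverse events are defined by onset date or by leading to premature discontinuation of study drug (Section 7.1.5.1).
- Treatment-emergent laboratory abnormalities rest on DAIDS toxicity grades (Sections 7.2.1 and 7.2.1.1), and the labels in Appendix 2, item 12, include no microbiology test.
- No visible listing sets baseline against postbaseline coinfection.
- The postbaseline rule picks the record closest to the nominal day first for these tests. Worst severity decides only ties on that day.

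**Conclusion.** The point holds as a minor flaw in a stated rule. Read literally, Section 3.8.3 turns a discordant same-day baseline influenza or RSV pair into a negative, and the Section 5.2 listing can then show 'None' for a child in whom the virus was detected that day.

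Its reach is one descriptive listing column in an uncommon situation. It does not touch a primary or secondary endpoint, the treatment-emergent definitions or any formal test. The listed status is wrong only when the positive result is true. The percentages in the working rest on assumed sensitivity, specificity, prevalence and independence, and show direction and possible size, not an expected count. The statement that no output would show on-treatment acquisition is limited to the unredacted text.

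**What to change.** In Section 3.8.3, widen the baseline bullet for SARS-CoV-2 infection status so that it also names influenza A, influenza B and RSV, with a positive result selected when same-day records disagree. Leave lowest severity in place for the other categorical (safety) data.

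An alternative is to show all same-day results for these viruses in the listing. That avoids choosing between the two errors and suits a report made only of listings.

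The cost is one line of wording and no new data. Two limits should be accepted knowingly:

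- With any positive counting, a single false positive is listed as a coinfection. The SAP already accepts this for SARS-CoV-2.
- The change covers same-day records only. Screening may precede baseline by up to 48 hours (Appendix 1, footnote a), so a positive on an earlier day followed by a Day 1 negative would still be listed as 'None' under the last-value rule.
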